#### ***Exclusion criteria***

- Cardiorespiratory disorders
- Associated cerebral disease
- Psychiatric illness
- Electrolyte and hormonal imbalance
- History of drug abuse

- Postoperative meningitis
- Administration of high dose steroids

### **Randomization and blinding**

Randomization will be done using computer-generated random numbers. The patient will be randomized to receive isoflurane or desflurane anaesthesia prior to surgery. All the patients involved in the study will be blinded to group allocation. The physician administering anaesthesia will be presented with envelopes containing the random numbers with the assigned groups just prior to surgery. The investigator will be blinded to group allocation.

### **Anaesthesia Protocol**

All the preoperative medications will be continued on the day of surgery. Anaesthesia will be induced with propofol 2-2.5 mg/kg and fentanyl 2 ug/kg. Vecuronium 0.1 mg/kg will be used to facilitate endotracheal intubation. All the patients will be monitored with 5 lead electrocardiogram, pulse oximeter, non-invasive blood pressure, temperature, airway gas levels, end-tidal carbon-dioxide concentration and urine output. Maintenance of anaesthesia will be carried out with either isoflurane or desflurane as per the randomization. The depth of anaesthesia will be monitored using entropy (to keep state entropy between 40 and 60). Analgesia will be maintained with fentanyl 0.5-2 ug/kg/hour and Vecuronium 0.06 mg/kg will be used intermittently for neuromuscular blockade to maintain less than two twitch response on neuromuscular transmission (NMT) monitoring. Replacement fluid will consist of normal saline. Intraoperative haemodynamics, oxygen saturation, temperature and blood loss will be recorded and compared among the two groups. The patients will be administered an antiemetic intraoperatively. At the end of the procedure neuromuscular blockade will be antagonized with neostigmine (0.05mg/kg)

and glycopyrrolate (0.01mg/kg). The patients who cannot be extubated at the end of the procedure will followed up in the postoperative period. The patients who cannot be extubated within forty-eight hours following surgery will be excluded from the study.

### **Study protocol**

The screening for preoperative cognitive dysfunction will be done using the mini-cog test which includes a three word recall test and clock drawing test. The patients with preoperative cognitive dysfunction will also be included. The primary outcome variable will be assessment of delirium at day one and day three following surgery. Post operative delirium will be diagnosed using the 3D-CAM(Confusion Assessment Method) which tests for four features with a series of questions. The features include 1) acute onset and fluctuating course,2) inattention,3) disorganized thinking and 4) altered level of consciousness. Diagnosis of delirium is made if features 1 and 2 and either 3 or 4 are present. Similarly the severity of POD will be assessed on day one and day three following surgery. Severity of postoperative delirium will be assessed using the CAM-S long form delirium severity score.It asseses ten features including 1) acute onset and fluctuating course,2)inattention,3)disorganized thinking , 4)altered level of consciousness, 5) disorientation, 6)memory impairment ,7)perceptual disturbances ,8)psychomotor agitation, 9)psychomotor retardation and 10) altered sleep-wake cycle. The scores range from 0 to 19.

The demographic data of the patients,type and site of surgery will be noted. Preoperative hemoglobin, serum electrolytes, blood urea and serum creatinine will be recorded. The average of 3 blood pressure (BP) readings measured preoperatively will be recorded as baseline. Intraoperative hemodynamics will be monitored using non invasive blood pressure monitoring. Systolic BP <30% of baseline will be recorded as hypotension and systolic BP >30% will be

recorded as hypertension. The management of intraoperative hypotension and hypertension will be at the discretion of the attending anaesthesiologist. The intraoperative factors like duration of surgery and anaesthesia, use of intravenous fluids , blood loss, number blood units transfused and opioid use will be studied at the time of surgery. The time to emergence and extubation following the completion of surgery will be noted. Emergence time will be the time from cessation of anesthetic agent to the time the patient responds to verbal commands. Extubation time will be the time interval between cessation of anesthetic agent and extubation of trachea.

The postoperative factors like postoperative pain, nausea and vomiting, fever, hemoglobin, serum electrolytes, blood urea and serum creatinine will be noted.

Preoperative and postoperative pain will be assessed using the numerical rating score on a scale of one to ten.

The association of various preoperative, intraoperative and postoperative factors with POD will be determined.

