Desflurane is associated with faster emergence and lesser incidence of postoperative cognitive dysfunction compared to isoflurane. Animal studies have shown that prolonged exposure to isoflurane to be neurotoxic. We hypothesize that the adverse neurological outcomes associated with isoflurane compared to desflurane may be associated with an increased incidence of postoperative delirium. Hence we are conducting this study to compare the occurrence of postoperative delirium with Isoflurane and Desflurane in spine surgery patients.

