## STATISTICAL ANALYSIS

All analysis will be done using SPSS version 22 (SPSS Inc., Chicago, IL, version 16.0 for Windows). Descriptive statistics will be obtained for demographic patient related and treatment related variables. The variance between both the treatment groups will be analysed using two way ANOVA. The primary end points will be compared between the two groups using chi square statistics. As a secondary outcome measure, univariate and multivariate analysis will be done to identify the factors that may influence post operative delirium.

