### 2. Intraoperative Period

- a) The attending anaesthesiologist will be briefed about the anaesthesia protocol. The random number sealed envelope containing the randomized study group will be handed over to the anaesthesiologist.
- b) The attending anaesthesiologists will administer the anaesthetic agent as per the randomization.
- c) Factors including duration of surgery and anaesthesia, intravenous fluids used, intra operative blood loss, number of blood units transfused, intra operative hemodynamics, intra operative opioid use ,time to emergence and time to extubation will be noted.

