### 3. Postoperative Period

The patients will be followed up on day one and day three following surgery. The patient will be subjected to psychological tests for evaluating delirium. Pain scores will be assessed using the numerical rating score. Postoperative factors like nausea and vomiting, fever, hemoglobin, serum electrolytes, blood urea and serum creatinine will be noted.

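### Aim 2 relates postoperative factors to delirium without requiring that they precede it, so the planned analysis cannot tell influences from consequences

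*Combined protocol and SAP*

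**What the plan says.** All references are to the combined protocol and SAP.

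- **Outcome timing.** Study protocol section: "The primary outcome variable will be assessment of delirium at day one and day three following surgery".
- **Factor timing.** Organization of Work Elements, 3. Postoperative Period: "The patients will be followed up on day one and day three following surgery". The same paragraph continues "Pain scores will be assessed using the numerical rating score" and "Postoperative factors like nausea and vomiting, fever, hemoglobin, serum electrolytes, blood urea and serum creatinine will be noted". It gives no separate time or lag for these measurements.
- **Planned use.** Study protocol section: "The association of various preoperative, intraoperative and postoperative factors with POD will be determined". Statistical Analysis section: "univariate and multivariate analysis will be done to identify the factors that may influence post operative delirium". The second item under Aims of the Study also speaks of factors able to influence delirium.
- **Emergence and extubation times.** 2. Intraoperative Period ends its list of recorded factors with "intra operative opioid use ,time to emergence and time to extubation will be noted". The Introduction states that "Desflurane is associated with faster emergence and lesser incidence of postoperative cognitive dysfunction compared to isoflurane".

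The plan gives no covariate list, model type or selection rule. It does not say whether the randomised arm is in the multivariable model, or which day's factor values are set against which day's delirium rating.

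**The concern.** A factor can be called an influence on delirium only if it came first. Here the postoperative factors and the outcome are observed together. A patient rated as delirious has, by the plan's own diagnostic rule, inattention plus disorganised thinking or an altered level of consciousness, and that patient is asked at the same follow-up to score pain on a numerical scale. A higher score among delirious patients could mean that pain contributed to delirium, that delirium changed the report, or both. Nothing in the plan stops a day-three value from being used to explain delirium already present on day one.

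A second, weaker strand concerns emergence and extubation times. They arise after randomisation and, by the plan's own account of emergence, depend on the agent. Offered as candidate factors, they may stand in for the arm.

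At stake is the second of the trial's two aims: its report could list consequences of delirium, or markers of the assigned agent, as influences.

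**Working it through.** **1. Timing.** Each postoperative value and each delirium rating belongs to day one or day three, which gives four pairings:

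| Factor value | Delirium first detected | Order |
|---|---|---|
| Day 1 | Day 1 | Same follow-up, unknown |
| Day 1 | Day 3 | Factor recorded before detection |
| Day 3 | Day 1 | Factor recorded after the outcome |
| Day 3 | Day 3 | Same follow-up, unknown |

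Only one pairing has a usable order, and the plan does not restrict the analysis to it.

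**2. Expected events.** The plan gives no figure for aim 2; its only relevant figure is N = 60. That reproduces as one-sided superiority over the 5-point margin: 0.27 × 0.73 × (1.645 + 1.036)² / (0.27 − 0.05)² = 29.3, so 30 per arm. In 60 patients, the spine-surgery incidence cited in the Introduction gives 60 × 0.033 = 2.0 to 60 × 0.038 = 2.3 events. The planning rates (0% and 27%) give 30 × 0.27 = 8.1. I use 2, 4 and 8 events, with 4 as an intermediate value.

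**3. How often pain would be flagged.** Assumptions, not in the documents: delirium raises the pain score by 1 or 2 points, the SD is 2, pain has no causal effect, and the test is a two-sided t-test at 5% with 58 degrees of freedom (critical value 2.002). With m events, the noncentrality is (shift / 2) × √(m(60 − m)/60).

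| Events m | √(m(60 − m)/60) | Noncentrality, 1 / 2 points | Flagged, 1 / 2 points |
|---|---|---|---|
| 2 | 1.390 | 0.695 / 1.390 | 10.5% / 27.7% |
| 4 | 1.932 | 0.966 / 1.932 | 15.8% / 47.6% |
| 8 | 2.633 | 1.317 / 2.633 | 25.4% / 73.5% |

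A separate simulation of trials of 30 + 30, with a 0.8 SD shift and at least two events, flagged pain in 53–56% of trials at the planning rates. It flagged pain in 24–25% with delirium at 3.5% in both arms or 2% against 5%.

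**4. Emergence time without arm.** In the same simulation emergence time differs between arms by an assumed amount and has no effect of its own on delirium. At 0% against 27% delirium it is univariately significant in 26% (1 SD), 42–45% (1.5 SD, two runs) and 60% (2 SD) of trials. Adjusting for arm brings this back to about 5%. At 3.5% in both arms, or 2% against 5%, the univariate rate at 1.5 SD is only 5–6%.

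**5. Emergence time with arm.** For an arm separation of d SDs, its correlation with arm is r = (d/2)/√(1 + d²/4), and the standard error for arm grows by 1/√(1 − r²) in a linear model.

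- d = 1: r = 0.45, growth 12%.
- d = 2: r = 0.71, growth 41%.

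These are linear approximations. In a large logistic simulation (27% against 5%, assumed) the growth was about 8% and 28%. The arm log-odds ratio did not move (1.94 with and without adjustment at 1 SD; 1.95 with and without at 2 SD).

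**The case against.** The case against has several sound parts.

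- **The language is hedged and exploratory.** The Study protocol section says association, and the Statistical Analysis section says only that factors may influence delirium. In the pain illustration the association is real, so reporting it as one would be correct; the nominal 5% is the comparator only for a causal reading. This stands, but the second aim and the Statistical Analysis section both invite that reading.
- **Postoperative factors have a stated rationale.** The section on risk factors for postoperative delirium names severe acute pain, postoperative transfusion and a low postoperative haematocrit. That justifies collecting such variables but does not establish time order. Haemoglobin and creatinine are much less plausible consequences of delirium than pain.
- **The pain figures are illustrative.** They are univariate, rest on an assumed shift and SD, and are smallest at the incidence the plan cites for spine surgery. All of this stands.
- **Intraoperative variables also follow randomisation.** True of opioid use or hypotension, for example. They precede the outcome, so reverse causation does not arise, but the arm coefficient in a model containing them need not be the total effect of the agent. That effect should be read from the primary comparison.

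A reader might also infer that the model is specified to use emergence time and will report it as an influence. The documents do not support that: the time is recorded, not named as a covariate, and the Study protocol section notes it apart from the intraoperative factors to be studied. Nor do they support the claim that including it biases the arm effect towards none. A pure proxy only widens the standard error; removing part of the effect requires emergence time to be a mediator, for which the documents give no evidence.

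**Conclusion.** The point holds for the postoperative factors. They share the day-one and day-three follow-up with the outcome, the plan commits to relating them to delirium, and no ordering rule exists, so the influence wording is not supported. Pain is the clearest case. Under the stated assumptions it would be flagged without being a cause in roughly 11–28% of trials at 2 events and 25–74% at 8.

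For emergence and extubation times the point is conditional. Used without arm, they may act as proxies, but only if delirium differs between the arms. Used with arm, they widen its standard error.

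It would be wrong to conclude that every postoperative variable is a consequence of delirium, or that the trial's main result is compromised. The primary chi-square comparison and the sample size do not depend on this analysis.

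**What to change.** In the Study protocol and Statistical Analysis sections, state that:

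1. The multivariable model contains arm and a few named preoperative and intraoperative factors that precede the outcome, without emergence or extubation time.
2. Day-one postoperative values are related only to delirium first detected after day one. Day-three values are never used to explain day-one delirium.
3. All other postoperative variables are reported as descriptive associations, not as influences.

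This needs no new data or patients. It leaves fewer candidate factors, which suits the roughly 2 to 8 expected events, and the lagged analysis in item 2 will use only part of those events, so it may be no more than descriptive. If one arm has no events, as the planning rates assume for desflurane, ordinary logistic regression gives no finite arm estimate. The SAP should name a method that copes, such as Firth's penalised likelihood.

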## **STATISTICAL ANALYSIS-**

Sample size calculation-

Incidence of POCD was 0% and 27% in a previously conducted study with 15 patients in each group with the use of desflurane and isoflurane respectively and the reported p value was 0.028.

We used these results to calculate sample size in our study to prove superiority of desflurane over

isoflurane with a margin of atleast 5 percent using an alpha error of 0.05 and power of 85%.The estimated sample size was 60 with 30 in each arm.

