## INTRODUCTION

In simple words delirium is defined as a temporary state of confusion . It is characterized by acute onset, fluctuating course, inattention, disorganized thinking, altered level of consciousness, perceptual disturbances, psychomotor disturbances, altered sleep-wake cycle, and emotional disturbances. Postoperative delirium (POD ) is disturbance of consciousness seen 24 to 72 hours after surgery. Its incidence varies from 5% to 15% but in high-risk groups such as cardiac and orthopedic patients, the range is 16–62%. Postoperative delirium is not only distressing for patient but also for family members. It is associated with functional decline, need for prolonged nursing care and prevent functional recovery. Hence it leads to prolonged duration of hospital stay and adds to morbidity and mortality in the long term. Exact mechanism responsible for POD is not known but several risk factors are found to be associated with POD. This includes patient related, surgery related and anesthesia related factors.

The incidence of POD in spine surgery in previous studies was found to be between 3.3% to 3.8%. Spine surgeries are associated with significant postoperative pain, blood loss, long duration of surgery and all these factors may be associated with POD after spine surgeries. But for the smooth conduct of spine surgery general anesthesia (GA) is required. During general anesthesia either inhalational volatile agents or intravenous hypnotic agents are used. However effect of the type of anesthetic agents in spine surgeries on postoperative delirium have not been studied previously. Both isoflurane and desflurane are commonly used inhalational agents. Now a days many centers prefer to use desflurane over isoflurane due to its low blood gas solubility which results in faster emergence. Among the inhalational volatile agents, previous studies have

compared the incidence of postoperative delirium with sevoflurane and desflurane especially in children and elderly individuals. But no study has compared the incidence of postoperative delirium with isoflurane and desflurane in middle aged adults undergoing spine surgery .

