### ***POST OPERATIVE DELIRIUM-***

American Psychiatric Association defines delirium as an acute change in cognition or disturbance of consciousness that cannot be attributed to a pre-existing medical condition, substance intoxication or medication. However various conditions such as age, functional status and substance abuse influence the risk of immediate and post operative delirium. Delirium in the

postoperative period can be divided into emergence delirium and post operative delirium depending on the time of presentation. Emergence delirium or emergence agitation is usually observed immediately after GA and is related to anesthetic drugs. It is common in children with peak age being 2-4 years. It is accompanied by psychomotor agitation which includes a series of unintentional and purposeless motion like pacing around a room, wringing ones hands, pulling off clothing, and self-extubation. It usually occurs within the first 10 minutes of recovery and resolves within minutes to hours without long term neurological effects. It is more commonly associated with less soluble inhalational anaesthetics like sevoflurane and desflurane.

Postoperative Delirium(POD) usually presents 24-72 hours following a lucid interval. It usually resolves within hours to days. Post operative delirium can have lasting effects beyond the perioperative period. POD has also been associated with postoperative depression, posttraumatic stress disorder-like syndrome which may impede recovery. As a result, delirium may have long-term mental health complications.

POD has been previously reported to occur following several kinds of surgery, including general surgery , head and neck cancer surgery, cardiac surgery , vascular surgery , hip fracture and joint replacement surgery.The incidence of post operative delirium(POD) in various studies ranges from 5% to 15%.Within certain high-risk groups such as hip fracture patients, the range is 16–62% with an average of 35%. The incidence of POD in spine surgery in previous studies was found to be between 3.3% to 3.8%.

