### ***RISK FACTORS FOR POSTOPERATIVE DELIRIUM-***

The mechanism of postoperative delirium is not clear. However ,studies have shown that major risk factors include age >70 years, pre-existing cognitive impairment, preoperative use of narcotics

or benzodiazepines, previous history of POD, alcohol abuse, breast and abdominal surgeries, long duration of surgery and preoperative cognitive dysfunction. Precipitating factors include: the use of physical restraints, malnutrition, the use of a urinary bladder catheter and electrolyte and fluid abnormalities. Specific perioperative risk factors include greater intraoperative blood loss, more postoperative transfusions, and postoperative haematocrit of <30%.

Severe acute pain regardless of the method of analgesia (opioid type, method and dose) is associated with POD. Certain types of injury, particularly hip fractures, and serious illness requiring intensive care are also associated with a high incidence of delirium^2. Several factors with positive correlation with POD may also suggest an association with preoperative anxiety.

Incidence of POD was greater with inhalational anesthetic agents than with propofol. Other risk factors of delirium include vision impairment, severe illness, cognitive impairment, and serum urea nitrogen: creatinine ratio of 18 or greater, vascular risk factors (tobacco use and vascular surgery), decreased cerebral perfusion, low preoperative executive scores and depressive symptoms, pre-existing attentional deficits in non-demented patients. Previous history of illness and long term treatment with antidepressants were associated with a decreased risk for POD.

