### **Selection of patients-**

#### ***Inclusion criteria***

- Patients scheduled for spine surgery.
- Age between 18-65 years
- American Society of Anaesthesiologists (ASA) Grade I and II patients
- Patients with Glasgow Coma Scale (GCS) of 15
- Postoperative Aldrette score > 9

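### The 85% power is for cognitive dysfunction at 27% vs 0%, not for delirium, the primary outcome; at the protocol's own spine-surgery delirium rate, power is about 2–19% two-sided

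*Combined protocol and SAP*

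**What the plan says.** The sample size calculation (Statistical Analysis) starts from an earlier study: "Incidence of POCD was 0% and 27% in a previously conducted study with 15 patients in each group", the 0% being desflurane and the 27% isoflurane. It aims at superiority of desflurane with a margin of at least 5 percent, alpha 0.05 and power 85%, and arrives at 60 patients, 30 per arm. It names neither the formula nor whether the test is one- or two-sided.

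The Study protocol section sets a different endpoint: "The primary outcome variable will be assessment of delirium at day one and day three following surgery", diagnosed by 3D-CAM. The methods paragraph of Statistical Analysis compares the primary end points by chi-square and mentions no margin.

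On how common delirium is, the protocol gives three ranges:

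- Spine surgery (Introduction, repeated in the Review of Literature): "The incidence of POD in spine surgery in previous studies was found to be between 3.3% to 3.8" (per cent).
- General and high-risk (Introduction): "Its incidence varies from 5% to 15% but in high-risk groups such as cardiac and orthopedic patients, the range is 16–62" (per cent).
- Hip fracture as the high-risk example (Review of Literature): "Within certain high-risk groups such as hip fracture patients, the range is 16–62% with an average of 35" (per cent).

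On who is enrolled, the inclusion criteria specify "Age between 18-65 years" and ASA I–II, and the exclusion criteria remove cerebral disease and psychiatric illness. The risk-factor section says "studies have shown that major risk factors include age >70 years, pre-existing cognitive impairment". The Study protocol adds: "The patients with preoperative cognitive dysfunction will also be included".

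**The concern.** Power belongs to an endpoint, an assumed pair of rates and a test. Here the rates come from one endpoint and the test is applied to another. The Review of Literature itself lists delirium and cognitive disturbances separately, and the Introduction offers a link between isoflurane's neurological effects and delirium only as a hypothesis. No delirium rate for either agent is given.

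The planning rate of 27% is about seven to eight times the only spine-surgery delirium rate in the protocol (27/3.8 = 7.1; 27/3.3 = 8.2). If the spine rate is nearer the truth, the trial will probably see too few cases to reach significance even if desflurane abolished delirium. A reader who trusts the 85% could then take a non-significant result as evidence that the two agents are alike.

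**Working it through.** **1. The plan's own figure.** Inputs from the sample size section: isoflurane p = 0.27 (or 4/15 = 0.267, since there were 15 patients per group), desflurane 0, alpha 0.05, power 85%, margin 0.05. Two methods lead to 30 per arm.

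- Superiority by a margin, unpooled normal formula, one-sided: n = (1.645 + 1.036)² × p(1 − p) / (p − 0.05)². This gives 29.3 for p = 0.27 and 29.9 for p = 4/15, so 30. The two-sided version gives 36.6 and 37.4.
- Two-sided Fisher exact test, no margin, p = 0.27: power is 83.5% at 29 per arm and 85.9% at 30. With p = 4/15 it is 85.0% at 30.

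So the arithmetic can be reproduced from the POCD inputs. The documents do not show which method was used.

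**2. What the planned test needs.** Assume one binary delirium outcome per patient, 30 per arm, no cases on desflurane and k on isoflurane.

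| k vs 0 | Pearson two-sided p | Fisher two-sided p |
|---|---|---|
| 3 | 0.076 | 0.237 |
| 4 | 0.038 | 0.112 |
| 5 | 0.020 | 0.052 |
| 6 | 0.010 | 0.024 |

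Uncorrected Pearson therefore needs 4 vs 0 two-sided. One-sided it needs 3 vs 0 (p = 0.038). Fisher two-sided needs 6 vs 0, and at these rates the continuity-corrected test has the same power as Fisher.

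**3. Power for delirium.** With desflurane at 0%, exact power is a binomial tail for X ~ Bin(30, p): P(X ≥ 4) for Pearson two-sided, P(X ≥ 3) for Pearson one-sided, P(X ≥ 6) for Fisher two-sided. Enumerating all 31 × 31 tables gives the same Pearson values. The documents do not report the anaesthetic mix behind 3.3–3.8%, so two readings are shown: (a) it is the isoflurane rate; (b) it is the average of the two arms, so isoflurane is 2 × 3.3–3.8% = 6.6–7.6%.

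| Isoflurane vs 0% | Pearson two-sided | Pearson one-sided | Fisher two-sided |
|---|---|---|---|
| 3.3% (a) | 1.6% | 7.5% | 0.04% |
| 3.8% (a) | 2.6% | 10.4% | 0.08% |
| 6.6% (b) | 13.3% | 31.8% | 1.2% |
| 7.6% (b) | 19.1% | 40.2% | 2.3% |
| 15% (top of general range) | 67.8% | 84.9% | 28.9% |
| 19% | 84.8% | 94.3% | – |
| 27% (POCD rate) | 97.8% | 99.4% | 85.9% |

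Two-sided Pearson power passes 85% at about 19% vs 0% (85.15% at 19.1%).

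**4. Expected cases in 60 patients.** (a) 30 × 0.033 to 0.038 = 1.0 to 1.1. (b) 60 × 0.033 to 0.038 = 2.0 to 2.3.

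**5. Patients per arm for 85% power** (exact, Pearson, vs 0%, no margin).

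| Isoflurane rate | Two-sided | One-sided |
|---|---|---|
| 3.3% | 181 | 142 |
| 3.8% | 157 | 123 |
| 6.6% | 90 | 71 |
| 7.6% | 78 | 61 |

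**6. The margin.** Read as percentage points, a 5-point advantage is impossible under (a): the largest possible difference is 3.3–3.8 points. Under (b) the largest difference exceeds the margin by only 1.6–2.6 points. The power figures above test zero difference, which is kinder to the plan than testing the margin.

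**7. What a likely result would say.** Newcombe 95% intervals for isoflurane minus desflurane: 1 vs 0 cases, −8.3 to +16.7 points; 2 vs 0 cases, −5.7 to +21.3 points.

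**The case against.** The strongest reply is that 3.3–3.8% may be the wrong benchmark. The protocol also cites 5–15% generally and 16–62% in high-risk groups, and 27% lies inside the latter. It argues that spine surgery brings pain, blood loss and long operations, and it admits patients with preoperative cognitive dysfunction. It reports a higher incidence with inhalational agents than with propofol, so if the cited spine studies used other agents, the isoflurane rate could exceed both readings. Nor does it say how delirium was measured in those studies. At 15% vs 0%, power is 68% two-sided and 85% one-sided.

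Part of this stands: the low figures, including the upper limit of 13–19%, are conditional on readings (a) and (b). It does not rescue the 85%. The sample size section invokes none of these delirium ranges. The spine figure is the only one specific to the operation, and an 18–65, ASA I–II population is not obviously high-risk when the protocol names age over 70 as a major risk factor. Even the top of the general range reaches 85% only one-sided and without the margin.

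Two smaller points are also fair. The plan does not say how day one and day three combine, so one binary outcome per patient is an assumption, though the natural reading of an incidence aim. And rewording does not add power; re-sizing would. Correcting the claim is the minimum. Enlarging the trial is the sponsor's choice, and the figures for it are in the working.

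**Conclusion.** The concern holds. The sample size arithmetic can be reproduced, but from the rates of a different endpoint, so the 85% is not the power of the primary comparison. At the protocol's own spine-surgery rate, the uncorrected chi-square would miss a complete absence of delirium on desflurane in 81–98% of trials two-sided, or 60–92% one-sided, across the two readings. Fisher or a continuity-corrected test would do worse.

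This rests on 30 evaluable patients per arm, no desflurane cases (the most favourable split), one binary outcome per patient, alpha 0.05, a null of zero difference, and 3.3–3.8% being either the isoflurane rate or the two-arm average. A substantially higher isoflurane delirium rate would raise the power, but the protocol offers no agent-specific evidence for one. The stated power should be corrected before it is relied on.

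**What to change.** In the sample size section, replace the power statement with text along these lines:

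> The 85% power refers to POCD rates of 27% (isoflurane) and 0% (desflurane). Method: [sponsor to state the formula, the sidedness and how the 5-point margin entered]. The primary outcome is delirium. With 30 per arm and no delirium on desflurane, exact power of the uncorrected chi-square test of zero difference at alpha 0.05 is 1.6–2.6% two-sided (7.5–10.4% one-sided) if the spine-surgery incidence of 3.3–3.8% is the isoflurane rate, and at most 13–19% (32–40%) if it is the average over both arms. At 15% vs 0% it is 68% (85%). The trial is not sized to show superiority by 5 points on delirium.

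If the sponsor has a delirium rate by agent, give it with its source and the power that follows.

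In the methods paragraph of Statistical Analysis:

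- State the sidedness, whether the test is Pearson, continuity-corrected or Fisher, and that it tests zero difference.
- Confirm that the power refers to one delirium outcome per patient, and how day one and day three form it.
- Report incidence per arm and the risk difference with a score or exact 95% confidence interval.
- State that a non-significant result will not be read as evidence of no difference.

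Cost: wording in two places and one routine interval, with no extra patients or visits. The stated power becomes much less favourable, and the claim to be sized for 5-point superiority on delirium is given up.
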